STUDY PROTOCOL
PADI
PANcreatitis and Diet

Randomized multicenter prospective clinical trial to compare the effectiveness of starting early oral diet versus Nil Per Oral in patients with acute pancreatitis

[name]
Consorti Sanitari del Garraf

Marzo de 2017

Introduction

Acute pancreatitis (AP) is a common condition in emergency services worldwide. Approximately 85% of AP are mild and the patients usually recover within 1 to 2 weeks, not requiring any critical care and organ support. The management of mild AP conventionally involves fasting, intravenous hydration and adequate analgesia until pain improves in order to prevent stimulation and allow the pancreas gland to rest. (1-7)

The current guidelines recommend the oral food intake should be tried as soon as possible, and beneficial effects or early enteral nutrition with mild AP have been reported in literature. (7-13)

Then, early oral refeeding (EOR) after mild and moderate acute pancreatitis (AP) is beneficial, but the optimal timing and starting criteria are unclear. Even now, refeeding after mild and moderate AP is typically started until clinical symptoms have resolved and pancreatic enzymes are decreasing, in a successively increasing manner. We aim to evaluate length of hospital stay and clinical findings for early refeeding with immediately full caloric intake in patients with mild and moderate AP.

Methods

Trial Design

This is prospective, randomized, controlled, multicentre trial. Patients with mild and moderate AP will be randomly assigned to groups A (EOR with low fat solid diet (LFSD), administration starting since admission in hospital) and B (fasting, until the symptoms, signs, inflammatory parameters of AP have resolved).

Study population

All patients diagnosed with AP with inclusion criteria and not exclusion criteria, will be informed of the possibility of taking part in the PADI study. After consent form (Annex 1) is signed, the patient will be randomized (Figure 1).

The diagnosis and severity of AP will be established according to the Modified Determinant-Based Classification.

Inclusion criteria

The inclusion criteria are: 1) diagnosed of AP by at least two of these three criteria: compatible abdominal pain, amylase or lipase level superior in three-fold respective laboratory baseline levels, and suitable findings in imaging techniques (CT, ultrasound or MRI); 2) age > 18 years, sign consent form.

Exclusion criteria

The exclusion criteria are: 1) pregnant or breastfeeding women; 2) abdominal pain lasting >96 hours before admission; 3) the possibility of poor oral intake for reasons other than AP; 4) Pancreatic neoplasm, endoscopic retrograde cholangiopancreatography or trauma etiology; 5) Chronic pancreatitis; 6) Randomization greater than 12 hours after admission.

Sample size

Given that historically the duration of hospitalization for mild AP at two hospitals is 7 days, a sample size of 120 patients (60 in each group) will be necessary to be recruited using a 10% drop-out rate, 80% power and 95% significance level to detect a two-day difference in total length of hospital stay between the study groups.

Randomisation

In each centre participants will be divided into two groups receiving one of the two study treatments. The allocation of participants to the different groups will be carried out based of predefined randomization lists created separately for each recruiting centre. The randomization lists will be prepared with a block size of 2 and with an allocation ratio of 1:1.

Duration

The planned starting date of the study is June 1st, 2017 and the planned finishing date of the study is December 31st, 2018.

Intervention

Based on the currently available guidelines, oral refeeding can be started early for patients with mild and moderate AP. Additionally, with an LFSD appeared safe and provided more calories. Therefore, both groups can be regarded as being treated within accepted practice recommendations. In this study, EORF with LFSD will be the intervention. Patients will be randomized to group A or PADI diet (EORF with LFSD) or fasting group.

Groups

In group A (PADI), the oral refeeding will be started after admission. Patients will receive a low fat solid diet with more and less 1500 calories, 35 g fat day.

In group B (fasting), the oral diet will be reintroduced in a traditional stepwise manner until the symptoms, signs, inflammatory parameters of AP have resolved.

General patient management

General treatment intimated by the IAP / APA guideline will be used.

All patients will receive adequate intravenous fluid resuscitation based on their individual hemodynamic parameters and fluid balanced. The patients will be monitored daily for gastrointestinal symptoms, abdominal pain, total intake/output, nutritional parameters, and laboratory findings.

Endpoints

The primary endpoint is length of hospitalization. Several secondary endpoints such as pain, the duration of fasting, tolerance to food, relapse rate, degree of transitional abdominal distension and/or abdominal pain and/or vomits after the first ingestion of oral food, multiorgan failure, pancreatic infection, hyperglycemia, nutritional parameters, mortality and quality of life will be determined to elucidate more detailed differences between the groups. The feasibility, safety and quality checks required for high quality evidence will be adhered.

Monitored parameters during hospitalisation

There will be a large variety of parameters monitored during the study: medical history, physical examination, laboratory test, diagnostic imaging, therapy, complications, interventions. The data collection will be done in the form A. This form will contain parameters collected on admission, parameters every day during hospital admission and contain parameters 1 month after hospital discharge.

Data management and statistical analyses

The investigator will ensure that the data in the form A are accurate, complete and legible. Detailed data flow will be described in a Data Management Plan. Data from completed form A will be validated under direction of the Data Manager according to a Data Cleaning

Plan. Any missing, or inconsistent recordings in the form A will be referred back to the investigator of each centre. The Data manager is a biostatistician.

Study populations

Three analysis populations will be defined:

Safety Analysis Set (SAS): all patients enrolled in the study.

Per Protocol Set (PPS): all enrolled patients who finished the study conforming to the requirements of the study protocol.

Intention to Treat (ITT): all randomized participants who start on a treatment, excluding consent withdrawals.

Withdrawal of a subject from Per Protocol Set

Any participants / investigators and Data manager can submit recommendations for dropouts from the PPS group with reasons given to the coordinator. The coordinator will discuss all the recommendations all the information and, if the alteration in the protocol would be expected to have any bearing on the interventions and outcomes of the study, the patient will not be included in the final pre-protocol analysis. Automatic dropout from per-protocol group shall be ordered if: 1) any of the exclusion criteria are diagnosed during the course of AP; 2) parameters for answering the primary endpoints are missed; or 3) serious medical reasons nor related to pancreatitis occur.

Applied software

Statistical analysis will be performed using SPSS 21 statistical packages. Pages Mac will be used for reporting.

Statistical methods

Baseline patient and disease characteristics will be analyzed using descriptive analysis. Demographic and baseline characteristics will be summarized for the overall study population. Continuous variables will be described by mean, median, SD and ranges and categorical variables will be described by absolute and relative frequencies. A graphical presentation of efficacy variables will be prepared. Descriptive statistics for both the primary and secondary parameters will be analyzed similarly. Mean changes (with 95% CI) from baseline to end-of-study visit will be presented. Chi-square test will be applied to compare proportions between the different groups. Survivals will be investigated using the Kaplan-Meier analysis method, while subgroup comparisons will be performed using the Chi-square or Fisher's exact test, as appropriate. For safety data, descriptive statistics and individual listing of adverse events will also be presented.

Centres

The trial will start in six centres:

1. Consorci Sanitari del Garraf - Hospital Residencia San Camil
2. Hospital Universitari Joan XXIII de Tarragona
3. Hospital Clinic de Barcelona

In all centre the coordinator will make an audit of the centre and will report to Data Manager.

Publication policy

Centres providing more than 20 patients can provide one authors to the authorship list. Every additional 20 patients will give the opportunity to nominate an additional author.

Feasibility and safety

The diet is a general protocol for the treatment of AP.

Since no unknown drugs/therapy are used in the study, no adverse or serious adverse events are expected that would be attributable to the intervention during the trial.

Discussion

We report a prospective, randomized, controlled trial to study the effects of EORF with LFSD in AP. The current studies and meta-analysis suggest that EORF should be beneficial but we don't know the optimal timing and starting criteria. Our main hypothesis is that EORF with LFSD is well tolerated and leads to a shorter total length of hospitalization. The aim of the study will be evaluated the efficacy and feasibility of immediate oral feeding as compared to traditional fasting in patients with mild and moderate pancreatitis.

Ethics

The study has been approved by the relevant organization: Comitè Ètic d'investigació d'la Fundació Union Catalana d'Hospitals. Codi CEIC 17/05.

Dissemination

This study will provide strong evidence as to whether EOR with LFSD is beneficial in the clinical management of mild and moderate AP. The results of this trial will be published in an open access way and disseminates among medical societies.

Conclusion

This study provides the stronger evidence concerning the optimal timing and starting criteria for EORF with LFSD.

References

3. Working Group IAP/APA Acute Pancreatitis Guidelines. IAP/APA evidence-based guidelines for the management of acute pancreatitis. *Pancreatol*. 2013;13(4 Suppl 2):e1-15. doi: 10.1016/j.pan.2013.07.063.

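### Fixed blocks of 2 within each centre make every second allocation deducible in advance in a trial with visible arms, exposing length of stay to selection bias

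*Combined protocol and SAP*

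**What the plan says.** The Randomisation section describes "predefined randomization lists created separately for each recruiting centre" and continues: "The randomization lists will be prepared with a block size of 2 and with an allocation ratio of 1:1". It gives no second block size and no random variation.

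The arms can be told apart at the bedside. Trial Design defines "groups A (EOR with low fat solid diet (LFSD), administration starting since admission in hospital" against fasting, and the Groups section describes a solid diet of about 1500 calories a day for the first arm. The text does not use the term open-label, but it describes no blinding of patients, staff or assessors. It also describes no way of concealing the lists. Figure 1, cited where randomisation is introduced, is not available to us and may add something.

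Partial safeguards exist. Under Study population, "All patients diagnosed with AP with inclusion criteria and not exclusion criteria, will be informed", and the patient is randomised only after signing consent. Under Centres, "In all centre the coordinator will make an audit of the centre". The primary endpoint is length of hospitalisation.

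**The concern.** In a 1:1 block of 2 the second allocation is always the opposite of the first. Hiding the list does not help, because the second assignment follows from the first and the block size is in the protocol.

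Eligibility and consent come before randomisation, so the entry decision can be made by someone who already knows the arm. Two routes are realistic:

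- not approaching a particular patient;
- stretching an exclusion that rests on judgement, namely "the possibility of poor oral intake for reasons other than AP".

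The numbered criteria also contain no severity limit, although Trial Design restricts the trial to mild and moderate disease, so some judgement about severity is left to the recruiter. Delaying a patient within the 12-hour entry limit is a minor route, as the working shows.

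If the arms differ in initial severity, they will differ in length of stay without any effect of diet. Covariate adjustment cannot fully remove selection on factors that were not measured.

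**Working it through.** **Inputs from the protocol.** Block size 2, ratio 1:1, lists by centre (Randomisation). 120 patients, 10% drop-out, 80% power, a 2-day difference (Sample size). June 2017 to December 2018, i.e. 19 months (Duration). Six centres stated, three listed (Centres). The SD of length of stay and the test for it are not given.

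**1. Predictability (exact; needs no SD or test).** For a block of 2b patients with known size:

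- Share of allocations fixed by earlier ones = 1/(b + 1). For b = 1 this is 1/2, so 120 × 0.5 = 60.
- Correct guesses for b = 1: the first of each pair is a coin toss and the second is certain, so (0.5 + 1)/2 = 75%, or 90 of 120.
- Incomplete blocks change little. If all six centres stop on an odd count, (120 − 6)/2 = 57 remain certain. With three centres at most two can be odd, giving (120 − 2)/2 = 59.

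| Lists | Certain | Correct guesses |
|---|---|---|
| Fixed 2 | 50% | 75% |
| Fixed 4, size known | 33.3% | 70.8% |
| Fixed 6, size known | 25% | 68.3% |
| Random 4 or 6, recruiter knows these two sizes are used | about 6% | about 69% |

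The first three rows are enumerated. The last is simulated with an optimal guesser.

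**2. Implied SD.** The plan's sample size cannot be reproduced without an SD, so I solved for it. Evaluable patients per arm = 60 × 0.9 = 54. With two-sided 5% assumed, SD = 2 / [(1.96 + 0.84) × √(2/54)] ≈ 3.71 days (3.68 with the t distribution).

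**3. Illustrative bias with no true effect.** Suppose steering shifts expected stay by η days in each known slot, downwards for diet and upwards for fasting. Half of each arm sits in known slots, so the false difference is η/2 + η/2 = η, multiplied by the fraction of known slots steered. The rejection rate comes from a two-sided t-test with 106 degrees of freedom and noncentrality bias / (SD × √(2/54)). For 1 day and SD 3.71 that is 1/0.714 = 1.40.

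| Scenario | η = 0.25 | η = 0.5 | η = 1.0 |
|---|---|---|---|
| All steered, SD 3.7 | 6% | 11% | 28–29% |
| All steered, SD 3 | 7% | 14% | 40% |
| All steered, SD 5 | 6% | 8% | 18% |
| Half steered, SD 3.7 | 5% | 6% | 11% |

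Simulation, which also counts the extra spread that steering creates, gives 26–27% for the 28–29% entry.

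**4. The same 1-day shift under random blocks of 4 and 6.** If the recruiter acts only on certain slots, bias = 2 × 0.06 × 1 ≈ 0.1 day and false positives stay near 5%. If the recruiter acts on every best guess and knows the sizes, bias = 2 × (2c − 1) × η, where c is the share of correct guesses. With c ≈ 0.69 this is about 0.75 day, with about 18% false positives. For blocks of 2 the same formula returns 1.0 day.

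**5. Delay route.** 120/19 = 6.3 enrolments a month, or 1.1 (six centres) to 2.1 (three centres) per centre. Assuming Poisson arrivals, the chance of another enrolment at the same centre within 12 hours is 1.7% to 3.4%.

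**The case against.** Five points can be made for the plan.

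- **Certainty is conditional.** The recruiter must know the block size, the previous arm at that centre, and whether the next slot opens or closes a pair. At 1.1–2.1 enrolments per centre per month, patients arrive roughly 14–29 days apart. Against a historical stay of 7 days, the next enrolment falls within 7 days only about 21–38% of the time, so the previous patient has usually gone home and prediction needs memory or notes. This stands as a qualification. A site investigator who keeps count still has what is needed.
- **The routes require a breach.** Not informing an eligible patient contradicts the protocol, and using the oral-intake exclusion to sort by pancreatitis severity would misapply it. That is true, but selection bias usually works in just this way. No screening log is described that would let an audit see who was not approached.
- **The magnitude is hypothetical.** The SD, the test, the size of the shift and the frequency of steering are all assumed. This stands, and the false-positive rates are only an illustration.
- **The remedy is partial.** Correct guesses fall only from 75% to about 69%, and a recruiter who acts on best guesses and knows the sizes keeps about three quarters of the bias. This stands too. Withholding the sizes should reduce it further, by an amount not quantified here.
- **An ethics amendment is needed**, since approval is already recorded. This is a real but small cost.

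**Conclusion.** The concern holds. Followed exactly as written, the plan uses the most predictable 1:1 permuted block there is, in a trial whose arms are visible. The figures of 50% certain allocations and 75% correct guesses are exact for complete blocks; at least 57 of 120 allocations remain certain if all six centres stop mid-block. They rest only on a recruiter who follows earlier allocations at the centre.

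What is established is exposure to selection bias, not that bias will occur. The effect on the primary comparison depends on assumptions the documents cannot settle, and ranges from negligible to a false-positive rate of about 40% (SD 3 days, 1-day shift, every known slot steered). The informing rule, consent before randomisation and the centre audit do not hide the next arm. Because the damage cannot be repaired after enrolment and prevention is cheap, the lists should be changed before the first patient is randomised.

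**What to change.** Replace the block-size sentence in the Randomisation section with:

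> Lists are stratified by centre, with an allocation ratio of 1:1 and randomly varying block sizes. The block sizes are held in a restricted document by the person who generates the lists and are not disclosed to sites. Each allocation is released only after consent and eligibility are recorded, centrally or by sequentially numbered opaque sealed envelopes.

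The sizes themselves (for example 4 and 6) belong only in the restricted document.

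The cost is regenerated lists, a simple release step and an amendment to a protocol that already has ethics approval. The protocol is dated March 2017 and the planned start is 1 June 2017, so on the documents' own dates this fits before enrolment.

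The statistical price is small. With blocks of up to 6 the final imbalance is at most 3 patients per centre, so at worst 6 × 3 = 18 across six centres. In simulation of 120 patients over three or six centres, the total imbalance was 4 or less in about 95% of trials.

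### Length of stay ends at a discharge decision for which the protocol states no criterion common to both arms, while the diet allocation is visible; whether readmission days count is a smaller point to clarify

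*Combined protocol and SAP*

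**What the plan says.** The primary endpoint is given in one sentence of the Endpoints section: "The primary endpoint is length of hospitalization". The Sample size section plans "to detect a two-day difference in total length of hospital stay between the study groups", starting from the statement that "historically the duration of hospitalization for mild AP at two hospitals is 7 days". The Discussion gives the expected direction: "EORF with LFSD is well tolerated and leads to a shorter total length of hospitalization". The word 'total' appears in the Sample size and Discussion sections and is defined in neither.

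The Trial Design section describes group A as early oral refeeding with a solid diet, "administration starting since admission in hospital", and group B as "fasting, until the symptoms, signs, inflammatory parameters of AP have resolved". The Groups section words group B differently: "the oral diet will be reintroduced in a traditional stepwise manner until the symptoms, signs, inflammatory parameters of AP have resolved". These two descriptions need to be reconciled, but on either one the resolution condition concerns diet and not discharge, and group A has no counterpart.

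For care common to both arms, General patient management says "General treatment intimated by the IAP / APA guideline will be used" and lists items to be monitored daily. The protocol text does not mention masking, who decides discharge, or readmission. Relapse rate is a secondary endpoint, and form A collects data 1 month after discharge.

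**The concern.** Discharge is a decision, and it fixes the value of the primary endpoint. Three features of this plan come together: the arm is visible to staff and patients, the protocol states which arm it expects to leave earlier, and no stated rule says when a patient in either arm is fit to go. If knowledge of the arm moved discharge by part of a day for reasons other than recovery, the primary comparison would move with it. Unless readiness is recorded during the stay in the same way in both arms, the analysis has nothing against which to judge such a shift.

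A shorter stay that results from earlier feeding is the treatment effect, not bias. The concern is only with a shift that has nothing to do with recovery.

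The undefined 'total' adds a smaller ambiguity. Two analysts could reasonably differ on whether days in hospital after a readmission belong in the primary endpoint.

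**Working it through.** **Inputs from the Sample size section.** Difference 2 days, 60 per group, 10% drop-out, 80% power. The stated 95% significance level is read as alpha 0.05, and two-sided testing is assumed because sidedness is not stated. Evaluable per arm: 60 × 0.9 = 54.

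**The plan's own figure.** The protocol gives no SD, so 120 cannot be reproduced from its inputs. Solving backwards:

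- SD = 2 / [(1.960 + 0.842) × √(2/54)] = 2 / (2.802 × 0.19245) = 2 / 0.5392 = 3.71 days.
- Forward check with SD 3.70: n = 2 × 3.70² × 2.802² / 2² = 53.7, so 54 per arm; 54 / 0.9 = 60 per arm; 120 in total.

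An SD of about 3.7 is thus what the plan implies, not what it states.

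**Effect of a discharge shift b when there is no true difference.** With SE = SD × √(2/54), the rejection rate of a mean-based test is 1 − Φ(1.96 − b/SE) + Φ(−1.96 − b/SE).

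For SD 3.71, SE = 0.714:

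- b = 0: 5.0%.
- b = 0.25: b/SE = 0.350; 0.0537 + 0.0104 = 0.064, or 6.4%.
- b = 0.5: b/SE = 0.700; 0.1039 + 0.0039 = 0.108, or 10.8%.

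Because the SD is not stated, a range for b = 0.5:

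- SD 3 (SE 0.577, b/SE = 0.866): 0.1370 + 0.0024 = 13.9%.
- SD 5 (SE 0.962, b/SE = 0.520): 0.07488 + 0.00658 = 0.08146, or 8.1%.

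The Statistical methods section names no between-group test for length of stay. A simulated Mann-Whitney test at SD about 3.7, mean 7 and b = 0.5 gives a similar 10.2% (normal data) or 11.4% (gamma data), so the choice of test hardly matters here.

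The shifts of 0.25 and 0.5 day are invented for scale. Half a day is a quarter of the two-day target (0.5 / 2).

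**Readmission.** The documents give no rate, so no effect can be estimated. For scale only, it would take 0.5 × 54 = 27 readmission days in one arm to move that arm's mean by half a day.

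**The case against.** The strongest reply is that the bias is conjecture. The protocol does not say who decides discharge, gives no hint that group A would be sent home early, and describes both groups in the Intervention section as treated within accepted practice. Any unmasked trial of this size with length of stay as its endpoint would produce the same figures. At the SD tied to this protocol, a quarter-day shift moves 5% only to 6.4%. This stands: the figures show sensitivity, not an expected error.

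A reader might infer that the trial has no discharge rule at all. The documents do not support that. The content of the guideline cited for general treatment is not available here, and form A, Figure 1 and the Data Management Plan are not reproduced. The absence can be claimed for the protocol text only.

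Separate 1:1 lists per centre balance differences in discharge habit between centres. That is correct, but it does not protect against a habit that differs by arm within a centre.

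On readmission, the plain reading of length of stay is admission to discharge. A reader might infer that relapses would be hidden from the trial, but an excess could still show in the secondary relapse rate. What remains is a clarification.

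Finally, a readiness date recorded by the same unmasked staff could carry the same bias. That also stands, and it limits what the fix can claim.

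**Conclusion.** The omission in the protocol text is clear; the size of any bias is unknown. The primary endpoint depends on a decision made with the arm visible, with no stated criterion shared by the arms, so a discharge shift unrelated to recovery is possible. If there were no true effect, a shift of 0.25 or 0.5 day would raise the false-positive rate from 5% to about 6.4% or 10.8%. These figures rest on 54 evaluable per arm, two-sided 0.05 testing, the implied SD of about 3.7 days and shifts that are purely hypothetical.

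A reader might go further and conclude that the primary result will be biased in favour of early feeding. The documents do not show this: they state an expected direction, which is not evidence that discharge would follow it. The point is best taken as a cheap improvement to make before the data are collected.

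**What to change.** 1. Prespecify one set of discharge-readiness criteria, identical in both arms. The investigators should set the clinical content, using objective items from those already monitored daily under General patient management. Apply the criteria to every patient each day, record on form A the date they are first met, and analyse time to readiness as a prespecified supportive analysis beside actual length of stay. If possible, have readiness assessed by someone unaware of allocation.
2. State that the primary endpoint is the index stay from admission to actual discharge. Add a prespecified sensitivity analysis of index stay plus readmission days up to the 1-month contact.

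The cost is some endpoint wording and one or two extra dates on form A; whether form A already holds them cannot be checked. The sample-size basis is unchanged if the historical 7 days was also measured from admission to discharge of the index stay. The protocol does not say so, so this is an assumption to confirm.

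Two limits should be acknowledged. Unless an assessor unaware of allocation can be found, readiness will still be dated by unmasked staff. If the criteria include oral tolerance, they will partly reflect the difference between the arms. The readiness analysis therefore reduces the risk of bias and helps interpretation, but it neither removes nor corrects a biased discharge date.

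### The set labelled Intention to Treat depends on an undefined post-randomisation condition, starting a treatment, which on one possible reading would fall on the diet arm only

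*Combined protocol and SAP*

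**What the plan says.** The section Study populations, under Data management and statistical analyses, defines three sets.

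- The Intention to Treat (ITT) set is "all randomized participants who start on a treatment, excluding consent withdrawals".
- The Safety set is "all patients enrolled in the study".
- The Per Protocol Set (PPS) is limited to enrolled patients who completed the study in line with the protocol.

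On the endpoint, the section Endpoints states: "The primary endpoint is length of hospitalization". No section says which set is used to analyse it.

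On the treatments, Trial Design describes group A's low-fat solid diet with "administration starting since admission in hospital". The section Groups adds: "Patients will receive a low fat solid diet with more and less 1500 calories, 35 g fat day". Group B fasts until the attack has settled. Neither section gives a first meal, a minimum intake or a time window that marks the start of treatment, or says who judges it.

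On eligibility, exclusion criterion 3 is "the possibility of poor oral intake for reasons other than AP". A patient who cannot eat because of the pancreatitis itself can therefore be randomised.

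**The concern.** An ITT set protects the randomised comparison because membership is fixed at randomisation. Here membership also depends on something that happens afterwards, and that event differs in kind between the arms. Fasting begins without any act by the patient. A solid diet does not, if starting it means eating it. No blinding is described, so whether a patient started could be judged with the arm and the clinical course known.

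Patients who cannot eat because of pancreatitis are likely to stay longer. Removing them from group A alone would shorten that arm's mean stay without any true effect, in the direction of the trial's main hypothesis. It would also remove informative patients from the secondary outcome "tolerance to food".

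**Working it through.** **1. Which readings lose patients?**

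| Reading of starting a treatment | Group A patient who never eats | Group B patient | Effect on the comparison |
|---|---|---|---|
| Eating the diet | Left out | Kept | Favours group A |
| Diet ordered or offered | Kept | Kept | About nil |
| Kept nil by mouth counts as a treatment | Kept | Kept | About nil |

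No time limit attaches to starting. Even on the first reading, a patient who cannot eat on day 1 but eats on day 3 has started. Only patients who never take the diet would be lost.

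**2. Does another set restore them?** The PPS requires conformity with the protocol, which implies having started, so it carries the condition too. Only the Safety set is free of it, and that set is not assigned to length of stay.

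**3. Inputs.**
- From Sample size: historical mean stay 7 days, target difference 2 days, 80% power, 60 per arm, 10% drop-out.
- Assumed: two-sided 5% level and a t-test, since the plan states no sidedness and names no test for length of stay.
- Assumed: no true effect, *k* group A patients lost, each with a stay of *L* days. The documents give neither *k* nor *L*.

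**4. The plan's own figure.** The plan gives no SD, so its sample size can only be solved backwards. Allowing for 10% drop-out, 60 × 0.9 = 54 per arm. A two-sided t-test with 54 per arm and 80% power detects a standardised difference of 0.544, so SD = 2 / 0.544 = 3.68 days. The normal approximation gives 3.71. With an SD of about 3.7, 54 per arm becomes 54 / 0.9 = 60 per arm, or 120 in total, as stated.

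**5. Bias and error rate.** With no true effect, the 60 group A stays sum to 60 × 7 = 420 days. After the loss:

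- group A mean = (420 − *kL*) / (60 − *k*)
- bias = 7 − group A mean
- SE = 3.68 × √(1/(60 − *k*) + 1/60), which is 0.68 for *k* = 3 and 0.67 for *k* = 1
- two-sided error = P(Z > 1.96 − bias/SE) + P(Z < −1.96 − bias/SE)

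| Lost from A | *L* (days) | Group A mean | Bias (days) | Share of 2 days | Error favouring A | Two-sided error |
|---|---|---|---|---|---|---|
| 3 of 60 | 10 | 6.84 | 0.16 | 8% | 4.2% | 5.6% |
| 3 of 60 | 12 | 6.74 | 0.26 | 13% | 5.8% | 6.7% |
| 3 of 60 | 14 | 6.63 | 0.37 | 18% | 7.8% | 8.4% |
| 1 of 60 | 10 to 14 | 6.95 to 6.88 | 0.05 to 0.12 | 3% to 6% | 3.0% to 3.7% | 5.1% to 5.4% |

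If one group B patient with the same stay is also lost beside three in group A, the group B mean falls as well, by the same formula with *k* = 1. The bias is then 0.11 to 0.25 day and the two-sided error 5.3% to 6.5%.

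**The case against.** The strongest reply is that the excluding reading is the least natural of the three.

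- The text says a treatment, not the allocated treatment, and fasting is one of the two study treatments. A group A patient kept nil by mouth has arguably started one.
- The protocol speaks of the diet being administered and received, which fits a diet that was offered.
- Tolerance of food is an outcome and feasibility of immediate feeding is an aim, so dropping patients who do not eat would defeat part of the trial's purpose.
- In mild and moderate disease, a patient who never eats during the whole stay should be uncommon.

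All of this stands as a reason for restraint. It does not remove the point: the plan does not choose between the readings, and the choice could be made after stays are known.

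A reader might infer three stronger things that the documents do not support.

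- That group A patients too ill to eat at first will be dropped. This needs the eating reading, and even then only those who never eat are lost.
- That the condition sits on the ITT set alone. The PPS implies it as well.
- That the false-positive rate triples. The rise from 2.5% to 7.8% is one tail only, in the most extreme case shown. The ordinary two-sided error goes from 5% to 8.4% there.

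**Conclusion.** The point holds in a limited form. The set called ITT carries an undefined post-randomisation condition that could, on one reading, act on group A only and favour it on the primary endpoint. On the other readings the effect is about nil. It is also not shown that the primary result would come from this set, because no set is named for length of stay.

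The documents do not show that a bias is likely, and its size is unknown. The 0.16 to 0.37 day illustration rests on an assumed count of non-starters, assumed stays and a back-solved SD. At 1 of 60 the effect is negligible. Severity is low to moderate: worth correcting because one sentence removes the risk, but not evidence of a biased result.

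**What to change.** 1. Define the ITT set as all randomised patients, analysed in the arm allocated, whether or not they ate. Exclude only those who withdraw consent to use of their data.
2. Name this set as primary for length of stay, with the PPS as supportive.

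The cost is protocol wording. Form A already records data on each hospital day, so nothing new has to be collected. If the sponsor meant that the diet was offered, nothing changes in practice.

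The downside is slight dilution. If 3 of 60 group A patients gain nothing from allocation, the two-day effect becomes 2 × (1 − 3/60) = 1.9 days. With SD 3.68, power falls from about 84% to 80% with 60 per arm, or from about 80% to 76% with 54 per arm, so about 4 points either way.
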